- •Psoriasis is a prevalent disabling and disfiguring dermatologic condition. WHO resolution on psoriasis has recognized the inadequate treatment options psoriasis patients suffer among other problems. The available treatment options have many side effects. A lot of the effective treatment options are either expensive or not appropriate for hepatic patients who represent a large subset of Egyptian psoriatic patients. This highlights the need for inexpensive and safe alternative.
- Few reports are published on the effectiveness of Turmeric in psoriasis treatment. Having an immune modulatory effect especially as anti NFkB it is expected to be effective therapy with minimal side effect.
- •Up to our knowledge this is the first study addressing the efficacy of combined turmeric and olive oil based topical therapy in psoriasis treatment.

Research question

What is the efficacy of Turmeric based topical therapy in the treatment of psoriasis?

Hypothesis

 Turmeric based therapy effectively treat psoriasis through reduction of NFκB expression in psoriatic skin.

Aim

The aim of this study is to verify the efficacy of Turmeric based therapy alone and combined with olive oil in the treatment of psoriasis.

Objectives

- 1- To evaluate the effectiveness of Turmeric extract based topical therapy for psoriasis
- 2- To compare the effectiveness of Turmeric extract based therapy and combined Turmeric/Olive oil based therapy.
- 3- To identify the effect of Turmeric based therapy of NFκB expression in psoriasis.

Subjects and methods

Technical design

• **Setting:** Dermatology, Venereology & Andrology Department, Faculty of Medicine Zagazig University, Pathology Department, Faculty of Medicine Zagazig University.

Study design:

• Type of study:

Clinical trial

• Sample size:

The sample size is calculated using OpenEpi with PASI score of the control group is 3.3 ± 2 and of the Turmeric treated group is 1.4 ± 1.1 . So at power of study 80 % and CI 95% the sample size is calculated to be 40 with 10 subjects in each group.

• Inclusion criteria

All participants must be willing to sign informed consent.

The study will include

For the patients group:

- 1- Patients with mild to moderate psoriasis vulgaris of any age & gender.
- 2- Patient didn't receive any systemic or topical therapy for psoriasis the last 4 weeks.

For the control group:

- 1- Psoriasis vulgaris patients (mild to moderate) of matching age and gender.

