- 2- Patients didn't receive any systemic or topical therapy for psoriasis the last 4 weeks

Exclusion criteria

- 1. Patients previously received topical or systemic therapy for psoriasis in the past 4 weeks.
- 2. Patients with pustular or erythrodermic psoriasis.
- 3. Patients with other dermatological diseases.

4. Patients have hypersensitivity from the active ingredients of the therapy.

Study groups

Four groups will be included in the study

Group 1: 10 psoriatic patients will receive Turmeric extract based topical therapy for at least 4 weeks up to 12 weeks.

Group 2: 10 psoriatic patients will receive Turmeric and Olive oil based topical therapy for at least 4 weeks up to 12 weeks.

Group 3: 10 psoriatic patients will receive only the base topical therapy for at least 4 weeks up to 12 weeks.

Group 4: 10 psoriatic patients will receive 2 sessions of NB-UVB every week for at least 4 weeks up to 12 weeks.

Group 5: 10 psoriatic patients will receive daily Betamethasone or Calcipotriol every week for at least 4 weeks up to 12 weeks.

Steps of study:

- All study subjects will be subjected to:
- I. History Taking: Detailed history will be taken from patients regarding name, age, duration of disease, arthropathy, family history of the disease, other dermatologic conditions, other systemic diseases and drug history
- II. Clinical evaluation: Assessment of the psoriasis using PASI score.
- III. *Dermoscopic evaluation*: The psoriatic plaques will be assessed using dermoscope. The dermsoccopic criteria of psoriasis includes dotted vessels regulary distributed on light red background with white silvery scales homogenously distributed on the erythematous background.

- IV. *Histopathologic assessment*: 5 ml punch Skin biopsies will be obtained and immersed in 10% formalin then embedded in paraffin wax and processed for H&E staining. The diagnosis of psoriasis will be histologically confirmed.
- V. *Immunohistochemical analysis*: NFκB expression in the psoriatic skin will be evaluated before and after treatment using immunohistochemical stain.

Administrative design

All patients included in the study will provide written informed consent after being informed about the study steps, the possible complications and their capability to withdraw at any time after approval of Institutional Review Board Of Faculty of Medicine, Zagazig University.

Results

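### The protocol states no rule for assigning patients to groups and lists controls separately as matched on age and gender, so every between-group PASI comparison is open to selection bias

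*Protocol*

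**What the plan says.** Under Study design, the Protocol gives the type of study in two words, as a clinical trial, with no word on allocation.

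Under Inclusion criteria there are two lists. The patients group is "Patients with mild to moderate psoriasis vulgaris of any age & gender". The control group is "Psoriasis vulgaris patients (mild to moderate) of matching age and gender". Both lists have the same disease, severity range and four-week treatment-free period, and the exclusion criteria are common to all. The matching phrase is the only real difference.

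Under Study groups, each group is defined by the treatment it gets, for example "Group 3: 10 psoriatic patients will receive only the base topical therapy" and "Group 4: 10 psoriatic patients will receive 2 sessions of NB-UVB every week". No sentence anywhere mentions randomisation, a sequence, concealment, alternation or any other route into a group.

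The comparisons that depend on this are stated plainly. The sample size uses "PASI score of the control group is 3.3 ± 2 and of the Turmeric treated group is 1.4 ± 1.1". The Aim reads "The aim of this study is to verify the efficacy of Turmeric based therapy alone and combined with olive oil". Objective 2 is "To compare the effectiveness of Turmeric extract based therapy and combined Turmeric/Olive oil based therapy". No group number is attached to the control group of either the inclusion criteria or the sample size.

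**The concern.** If patients were drawn from one pool and allocated at random, a second inclusion list would have little purpose. A list that defines controls by reference to other patients reads like a comparison group chosen to resemble a treated group. With no allocation rule beside it, nothing in the text prevents whoever enrols a patient from steering that patient to a particular group.

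Two things follow. First, where controls are matched, the match covers age and gender only. It does not balance the other characteristics that the Protocol records under History Taking ("duration of disease, arthropathy, family history of the disease", other systemic diseases, drug history), nor PASI within the mild-to-moderate range. Second, the missing rule affects comparisons that the matching phrase does not reach. Objective 2 sets Group 1 against Group 2, both treated, so it has no stated protection at all.

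At stake is whether a PASI difference can be put down to turmeric. A difference in who was placed in each group would produce the same kind of result, in either direction.

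**Working it through.** **The texts side by side.**

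| Question | What the Protocol states |
|---|---|
| Type of study | Clinical trial; allocation not described |
| Treated patients | Any age and gender |
| Controls | Age and gender to match |
| Route into Groups 1 to 5 | Not stated |
| Which group is the control group | Not stated; Group 3 (base only) is the natural candidate |
| Groups 1 and 2 against each other | Objective 2; not covered by the matching phrase |

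**The plan's own figure.** The Protocol gives no figure for bias. Its only related figure is the sample size of 10 per group. The usual two-sided formula with its inputs is n = (2² + 1.1²)(1.96 + 0.84)² / (3.3 − 1.4)² ≈ 11.3, so 12 per group rather than 10. That is a separate matter, and nothing below depends on it.

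**Illustration of how far a shift could mislead.**

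Inputs from the Protocol: 10 per group; control SD 2; control mean 3.3; 95% confidence, read as a two-sided 5% test.

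Assumptions: no treatment effect; SD 2 in both groups; a systematic difference b between the groups of 0.5, 1.0 or 1.5 PASI points. These are 15%, 30% and 45% of 3.3.

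Standard error of the difference = 2 × √(2/10) = 0.894. Noncentrality = b / 0.894. The false-positive rate is the chance that a noncentral t variable with 18 degrees of freedom falls beyond the two-sided 5% limits.

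| Assumed shift b | Noncentrality | False-positive rate |
|---|---|---|
| 0.5 | 0.56 | 0.083 (about 8%) |
| 1.0 | 1.12 | 0.185 (about 19%) |
| 1.5 | 1.68 | 0.355 (about 36%) |

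**Can the analysis repair it?** This was simulated with 40,000 runs per case, 10 per group, SD 2 at baseline and end, an assumed baseline-to-end correlation of 0.5, a shift of 1.0 and no treatment effect. With zero shift, all tests rejected in 0.049 to 0.051 of runs.

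| Where the shift lies | Baseline-adjusted model | Change from baseline |
|---|---|---|
| In baseline PASI, persisting to the end | 0.090 | 0.051 |
| In an unmeasured factor, seen only in end PASI | 0.219 | 0.185 |

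In the first row, the adjusted model keeps a bias of 1.0 × (1 − 0.5) = 0.5 points, while the change score removes it. In the second row neither method restores 5%. The result therefore depends on where the imbalance lies, which cannot be known when groups are formed by an unstated process.

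**The case against.** The strongest reply is that the matching phrase proves little. It does not say that controls are recruited later, paired or hand-picked. It also fits stratified or matched-pair randomisation, or a loose wish that groups be comparable. This stands. A reader might infer that the trial is non-randomised, or that matching contradicts random allocation. The documents do not support either: the Protocol is silent on allocation, and matching and randomisation can coexist. The phrase is a pointer to selected controls; the missing allocation rule carries the main weight.

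A second reply is that the statistical analysis plan is not shown and could add baseline adjustment. It could, and the Protocol leaves statistical methods open. But who enters which group is settled at enrolment and belongs in the protocol. The characteristics under History Taking are recorded for all subjects and can be described by group, although adjusting for all of them at 10 per group is limited.

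A third reply is that the error rates say nothing specific about this trial, since the shifts are assumed. That also stands, and they are offered only as a sense of scale. Higher rates would come from averaging the control SD with the turmeric SD of 1.1, but a setting with no treatment effect gives no reason to use the treated SD, so that calculation is not relied on.

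Finally, one might infer from the point that adjustment for baseline PASI should be required. The simulation does not support that: under non-random groups the adjusted model rejected more often than the change score in both cases. Nor does it show that the change score is generally right.

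**Conclusion.** The concern holds in this form: the Protocol does not say how patients reach any group, and its separate control list suggests selection by age and gender. Followed as written, every between-group PASI comparison is open to selection bias, including Objective 2. Matching on two characteristics does not remove it, and an analysis plan cannot repair it after enrolment.

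The document supports neither a size nor a direction for the bias. The rates of about 8%, 19% and 36% rest on the assumed shifts of 0.5, 1.0 and 1.5 points, on SD 2 in both groups and on no treatment effect. The conclusion does not depend on any of these values. It rests on the absence of an allocation rule, and it needs correcting before patients enter.

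**What to change.** 1. Use one eligibility list for all patients and delete the matching phrase. If balance on age and gender is wanted, make them stratification factors.
2. State that patients are allocated by a computer-generated random list with concealed assignment. Sealed, opaque, numbered envelopes are one option.
3. Name the group that is the control group of the sample size calculation.

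If randomisation is not possible, state how patients reach each group, call the study a non-randomised comparison and soften the aim of verifying efficacy. Leave the choice between a baseline-adjusted and a change-score analysis to the analysis plan.

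The Protocol announces four groups and lists five. That is a separate issue, but it has to be reconciled before a random list can be made.

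The cost is protocol wording, preparation of the list and a concealment method. No patients are added. Recruitment may be slower, because patients must accept any arm and the arms differ in burden; Group 4, for instance, attends for sessions every week.

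### The protocol announces four groups and 40 patients but lists five groups of 10, which is 50 patients

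*Protocol*

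**What the plan says.** The Sample size item under Study design bases its calculation on a comparison of two means: "PASI score of the control group is 3.3 ± 2 and of the Turmeric treated group is 1.4 ± 1.1". It concludes that "the sample size is calculated to be 40 with 10 subjects in each group".

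The Study groups section opens with "Four groups will be included in the study". Five numbered entries come after that line, all of the same form and each with its own 10 patients. The third, for instance, reads "Group 3: 10 psoriatic patients will receive only the base topical therapy for at least 4 weeks up to 12 weeks". The remaining entries cover these treatments:

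- first entry: topical turmeric extract;
- second entry: topical turmeric combined with olive oil;
- fourth entry: NB-UVB phototherapy;
- fifth entry: betamethasone or calcipotriol.

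The only between-group comparison named under Objectives is the second objective: "To compare the effectiveness of Turmeric extract based therapy and combined Turmeric/Olive oil based therapy".

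**The concern.** The number of arms and the total enrolment are basic design facts, and here the protocol gives each of them two values. The stated count and total fit each other but not the list.

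An investigator cannot comply with all three. Someone who recruits to the stated total at 10 per group must leave out one listed treatment, and the protocol does not say which. Someone who fills every listed group enrols 10 patients more than the protocol states. Those patients carry a real burden: the Steps of study section applies skin biopsy to all study subjects and has NFκB expression in skin assessed before and after treatment. The protocol also refers to Institutional Review Board approval, yet it offers no single enrolment figure to approve.

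The harm is operational. It concerns which treatments are run and how many people are enrolled. It does not change the power of any one pairwise comparison, since the group size is 10 throughout.

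**Working it through.** **Inputs, all from the protocol**

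| Quantity | Value | Section |
|---|---|---|
| Stated number of groups | 4 | Study groups, opening line |
| Stated total | 40 | Sample size |
| Stated size per group | 10 | Sample size |
| Groups listed | 5 | Study groups, list |
| Patients in each listed group | 10 | Study groups, list |

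**Step 1: reproduce the stated total.** Total = groups × patients per group = 4 × 10 = 40. This matches exactly, so the 40 was built on four groups.

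**Step 2: total from the list.** 10 + 10 + 10 + 10 + 10 = 5 × 10 = 50.

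**Step 3: size of the gap.** 50 − 40 = 10 patients, and 10/40 = 25% of the stated total.

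**Step 4: can the sample-size calculation settle which is meant?** A comparison of two means yields a number per group. The total depends on how many groups that number is multiplied by. With the protocol's inputs, the difference is 3.3 − 1.4 = 1.9 and the sum of variances is 2² + 1.1² = 5.21. The normal approximation at 80% power is

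n per group = 5.21 × (z_α + z_0.80)² / 1.9².

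The protocol gives a 95% confidence level but not whether the test is one- or two-sided, so I tried both at α = 0.05:

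- two-sided: n = 11.33, rounded up to 12; four groups give 48, five give 60;
- one-sided: n = 8.92, rounded up to 9; four groups give 36, five give 45.

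Neither version returns 40 or 50, so the calculation cannot arbitrate between them. These figures serve only that purpose here; whether 10 per group is adequate is not part of this point.

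**Step 5: can the rest of the protocol settle it?** The second objective needs Groups 1 and 2. The aim and objectives name none of Groups 3, 4 and 5. The inclusion criteria separate patients from a control group matched on age and gender, but do not say which listed group is the control. No text marks any group as optional, external or added later.

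**The case against.** The best counter-argument is about degree. Each listed group is fixed at 10 on either reading, no comparison loses power, and the repair is a matter of wording. The doubt can also be narrowed. The sample-size sentence sets a control against turmeric, and the base-only group is the natural control. If Groups 1, 2 and 3 are all kept, what remains uncertain is mainly whether Group 4 or Group 5 was intended. One might further guess that the last group was appended after the count was written.

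The point about power is correct and is accepted above. The narrowing is reasonable, but it is inference: no sentence labels Group 3 as the control, and nothing says that a group was appended. Even if that guess is right, the count and the total would still be wrong and would need to become five and 50.

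The usual innocent explanations do not apply. The five groups are separately numbered, complete sentences with different treatments, so this is not a broken table or a redaction. There is no amendment log, so neither statement is superseded text. A separate statistical analysis plan would not normally decide how many arms are enrolled, and it would not correct the protocol's own text.

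A related matter is weaker and carries no weight in the conclusion. The sample-size sentence speaks of one control group and one turmeric group, whereas the list has three groups without turmeric and two with it. That is missing detail, which an analysis plan might supply.

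**Conclusion.** The contradiction is real and must be corrected. The protocol states four groups and 40 patients and lists five groups and 50, a difference of one treatment arm and 10 patients (25% of the stated total). The conclusion rests only on counting the protocol's own entries and needs no outside figure or statistical assumption. The document does not show whether the list or the count is in error. The finding makes no judgement on which treatments belong in the trial.

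**What to change.** Reconcile the Sample size and Study groups sections so that the group count, the group list and the total agree. The sponsor decides which design is meant:

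- **Five groups intended:** change the count to five and the total to 50. The stated enrolment rises by 10 patients, with the biopsies and assessments that go with them.
- **Four groups intended:** keep the count and the total of 40, and remove one listed group.

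Either way, the text change is confined to two sections. The reconciled number should be the one put to the Institutional Review Board.

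It would be sensible in the same edit, before any results are seen, to say which listed groups the control and turmeric figures in the sample-size sentence refer to, or that they stand for a generic contrast. This is optional tidying and costs one sentence.

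### The protocol states four groups and 40 patients but lists five groups of 10, and Group 5 is one drug or another with no statement of which patients get which

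*Protocol*

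**What the plan says.** Three places in the protocol bear on this.

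- **Sample size.** The calculation takes "PASI score of the control group is 3.3 ± 2 and of the Turmeric treated group is 1.4 ± 1.1", "at power of study 80 % and CI 95"%, and concludes that "the sample size is calculated to be 40 with 10 subjects in each group".
- **Study groups.** The opening line is "Four groups will be included in the study". Groups 1 to 5 are then listed, each with 10 patients. Groups 1 to 3 receive turmeric, turmeric with olive oil, and the base alone. The fourth entry begins "Group 4: 10 psoriatic patients will receive 2 sessions of NB-UVB every week". The fifth reads "10 psoriatic patients will receive daily Betamethasone or Calcipotriol every week for at least 4 weeks up to 12 weeks" and is the only entry that offers a choice between treatments.
- **Objectives.** The only comparison of treatments named is "To compare the effectiveness of Turmeric extract based therapy and combined Turmeric/Olive oil based therapy". The other two objectives concern the effectiveness of turmeric therapy, with no comparator named, and its effect on NFκB expression.

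Neither Group 5 drug is mentioned anywhere else in the protocol.

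**The concern.** The number of arms and the number of patients are basic design facts, and here the document gives two incompatible versions of each. A reader cannot tell whether recruitment ends at 40 or 50, or whether all the listed arms will be run.

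The Group 5 entry adds a second uncertainty. It can mean that one drug, not yet named, is used for all ten patients. It can also mean that both drugs are used, with no numbers per drug and no rule for choosing. The wording does not even exclude a patient changing from one drug to the other during the treatment period. If both drugs are used and the choice is left open, it may follow the patient's condition. The arm's PASI result would then reflect an unknown mix of drugs and an unknown selection of patients, and a later breakdown by drug would rest on a handful of patients chosen by no stated rule.

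This is not a matter that a protocol can leave to an analysis plan. An analysis plan may say whether a mixed arm is analysed pooled or by drug, but what the arm receives is protocol content. Other provisions depend on it: the exclusion for hypersensitivity refers to the active ingredients of the therapy, and consent must cover the possible complications.

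**Working it through.** **Per-group figure.** Inputs from the Sample size paragraph: means 3.3 and 1.4, so a difference of 1.9; SDs 2 and 1.1; power 80%; confidence 95%. With the usual formula for two means,

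n per group = (SD1² + SD2²)(z for alpha + z for power)² / difference²
= (4 + 1.21)(1.960 + 0.842)² / 1.9²
= 5.21 × 7.85 / 3.61 = 11.33, so 12 (two-sided, normal approximation).

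A two-sided t-test needs 12.37, so 13. A one-sided normal calculation needs 8.92, so 9, and a one-sided t-test 9.68, so 10. The stated 10 is therefore in the neighbourhood, and exact on the one-sided t-test. The protocol does not state sidedness. Nothing below depends on this figure, and I take 10 per group as given.

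**Total.** A two-group formula yields a number per group; the total then depends only on how many groups there are.

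| Source in the protocol | Groups | Per group | Total |
|---|---|---|---|
| Sample size paragraph, with the opening line of Study groups | 4 | 10 | 4 × 10 = 40 |
| List under Study groups | 5 | 10 | 5 × 10 = 50 |

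Difference: 50 − 40 = 10 patients, exactly one listed group; 10/40 = 25% of the stated total.

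**Group 5.** No arithmetic settles this, so the readings are set side by side.

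- *One drug for all ten.* The arm is coherent, but the drug is unnamed. The defect ends once it is named.
- *Both drugs.* If each patient stays on one drug, the expected arm mean is w × A + (1 − w) × B. Here w is the share of patients on the first drug, and A and B are the mean results on each drug. The protocol gives none of w, A or B. If the choice of drug depends on the patient's condition, A and B also describe differently selected patients, so even a known w would not separate drug from patient. The size of the effect cannot be derived from the document and could be nil.

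**Reach.** Groups 1 to 4 each have a single defined treatment or fixed combination, so the open choice in Group 5 does not alter comparisons among them.

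**The case against.** The strongest reply is that little hangs on Group 5. No objective names it, the protocol never proposes a conclusion about either drug, and a pooled arm of conventional topical treatment would be a reasonable comparator. Most of this stands. It limits the second defect to comparisons with Group 5 and makes it a matter of definition rather than a threat to the stated objectives. It does not remove the defect, because the protocol nowhere declares a pooled arm and gives no rule for forming one. It also does not touch the contradiction in counts.

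It may also be said that the two matters are separate. They are: correcting the count would leave the choice of drug open, and the reverse. The 10-patient excess therefore measures only the first and lends no weight to the second.

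Four stronger readings are tempting, and the document does not support them.

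- A reader might infer that Group 5 is the arm that the total of 40 leaves out. The protocol does not say which group is omitted.
- A reader might infer that the turmeric comparisons are compromised. Those arms are defined without reference to Group 5.
- A reader might put a size on the mixture, either by trying out splits of the ten patients or by applying the planning difference of 1.9 to Group 5. No split is given, and the 1.9 was stated for turmeric against control, not for this arm.
- A reader might see a conflict between daily use and the weekly wording in the same entry. It reads most naturally as daily use in each week, and I do not count it.

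**Conclusion.** The point holds in two parts of different strength.

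First, the stated group count and total contradict the listed design: 40 against 50 patients, a gap of 10 or 25% of the stated total. This rests only on the protocol's own figures and needs no assumption.

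Second, the content of Group 5 is not settled. If both drugs are used as the text permits, the arm's result describes an uncontrolled mixture and supports no conclusion about either drug. This is conditional on both drugs being used, is confined to comparisons with Group 5, and cannot be quantified from the document. It does not show that any stated objective fails. Settling it would also not settle how patients are allocated between the groups, which is a separate question.

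The sponsor should make both corrections.

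**What to change.** 1. Reconcile the Sample size paragraph, the opening line of Study groups and the list of groups. At 10 per group, five intended arms mean stating five groups and 50 patients; four intended arms mean keeping 40 and saying which listed group is not part of the study.
2. State what Group 5 receives. The choice is the sponsor's, and none is preferred here.
3. If both drugs remain, declare the arm a pooled conventional-topical comparator, fix in advance how patients are assigned between the drugs, and state that no conclusion will be drawn about either drug alone.

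The cost is an amended Group 5 entry and a consistent count and total. Defining Group 5 adds no patients to the 50 already listed. Against the stated 40, running all five arms at 10 each needs 10 more patients, which the sponsor has to accept or avoid openly. The downside is a restated total, and conclusions from Group 5 limited to the arm as defined.
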